5.1.2.6 Week 156; Last Treatment Visit (Visit 40)

- 1. Administer SF-36v2 (should be completed prior to any clinical assessments)
- 2. Perform physical examination
- 3. Perform ECG
- 4. Take vital signs (within 15 minutes of the beginning of the investigational product infusion)
- 5. Record concomitant medications
- 6. Collect predose blood samples for:
 - Serum chemistry
 - Hematology
 - Hepatitis B virus DNA PCR TaqMan (Subjects with isolated hepatitis B core antibody positivity during Study CD-IA-MEDI-546-1013 or at any time for the

duration of this study will be tested monthly for HBV DNA. To remain eligible for this study, the subject's HBV DNA levels must remain undetectable as per the central lab [ie < 29 IU/mL HBV DNA detected])

- QFT-GIT test (only if negative or if indeterminate at any visit during Study CD-IA-MEDI-546-1013)
- SLEDAI-2K-associated lab tests (C3, C4, CH50, anti-dsDNA)
- Immunology profile (ANA, extractable nuclear antigens [RNP, Sm, SSA, SSB], quantitative immunoglobulins)
- Pharmacokinetics (MEDI-546 serum concentration)
- Pharmacodynamics (type I IFN signature with 21-gene assay)
- Immunogenicity (ADA to MEDI-546)
- Proteomics/biomarkers (optional)
- 7. Collect urine sample for:
 - Urinalysis
 - Urine β-HCG; dipstick (females of childbearing potential only, ensure result is negative)
 - SLEDAI-2K-associated lab tests: urine protein/creatinine ratio
- 8. Assess worsening and/or flare of SLE disease activity using SLE Increase in Disease Activity CRF and complete for SLE related AEs that are not serious, if applicable
- 9. Perform SLEDAI-2K
- 10. Evaluate subject for signs and symptoms of TB using a TB surveillance form
- 11. Administer investigational product
 - Take vital signs (BP, pulse, respiration, and temperature) approximately every 15 (± 5) minutes during the infusion, immediately after completion of the infusion, approximately 30 (± 5) and 60 (± 5) minutes after completion of administration of investigational product, and every 30 (± 5) minutes thereafter or until stable and ready for discharge (as judged by the investigator).
- 12. Assess for AEs/SAEs/AESIs (nonserious AEs will only be captured during the first year of the subject's participation in the study; however, nonserious AEs that result in interruption of investigational product and/or discontinuation from the study will be captured at any time during the subject's participation in the study)

5.1.3 Follow-up Period

5.1.3.1 28 Days after the Last Dose (+/- 7 Days): First Safety Follow-up Visit or Early Discontinuation Visit (Visit 41)

- 1. Record concomitant medications
- 2. Take vital signs
- 3. Collect blood samples for:

- Serum chemistry
- Hematology
- SLEDAI-2K-associated lab tests (C3, C4, CH50 complement, anti-dsDNA)
- Immunology profile (ANA, extractable nuclear antigens [RNP, Sm, SSA, SSB], quantitative immunoglobulins)
- Pharmacokinetics (MEDI-546 serum concentration)
- Pharmacodynamics (type I IFN signature with 21-gene assay)
- Immunogenicity (ADA to MEDI-546)
- Proteomics/biomarkers (optional)
- 4. Collect urine sample for:
 - Urinalysis
 - Urine β-HCG (dipstick; females of childbearing potential only, ensure result is negative)
 - SLEDAI-2K-associated lab tests: urine protein/creatinine ratio
 - Urine biomarker (optional)
- 5. Perform SLEDAI-2K
- 6. Assess worsening and/or flare of SLE disease activity using SLE Increase in Disease Activity CRF and complete for SLE related AEs that are not serious, if applicable.
- 7. Evaluate subject for signs and symptoms of TB using a TB surveillance form
- 8. Assess for AEs/SAEs/AESIs (nonserious AEs will only be captured during the first year of subject's participation in the study; however, nonserious AEs that result in interruption of investigational product and/or discontinuation from the study will be captured at any time during the subject's participation in the study)

5.1.3.2 59 Days after the Last Dose (+/- 7 Days): Second Safety Follow-up Visit (Visit 42)

- 1. Record concomitant medications
- 2. Take vital signs
- 3. Collect urine sample for:
 - Urine β -HCG (dipstick, females of childbearing potential only, ensure result is negative)
- 4. Assess worsening and/or flare of SLE disease activity using SLE Increase in Disease Activity CRF and complete for SLE related AEs that are not serious, if applicable
- 5. Evaluate subject for signs and symptoms of TB using a TB surveillance form
- 6. Assess for AEs/SAEs/AESIs (nonserious AEs will only be captured during the first year of subject's participation in the study; however, nonserious AEs that result in interruption

of investigational product and/or discontinuation from the study will be captured at any time during the subject's participation in the study)

5.1.3.3 85 Days after the Last Dose (+/- 7 Days): Third Safety Follow-up Visit (Visit 43)

- 1. Administer SF-36v2 (should be completed prior to any clinical assessments)
- 2. Record concomitant medications
- 3. Take vital signs
- 4. Perform ECG
- 5. Collect blood samples for:
 - Serum chemistry
 - Hematology
 - Lipid profile
 - SLEDAI-2K-associated lab tests (C3, C4, CH50, anti-dsDNA)
 - Immunology profile (ANA, extractable nuclear antigens [RNP, Sm, SSA, SSB], quantitative immunoglobulins)
 - Pharmacokinetics (MEDI-546 serum concentration)
 - Pharmacodynamics (type I IFN signature with 21-gene assay)
 - Immunogenicity (ADA to MEDI-546)
 - Proteomics/biomarkers (optional)
- 6. Collect urine sample for:
 - Urinalysis
 - Urine β-HCG (dipstick; females of childbearing potential only, ensure result is negative)
 - SLEDAI-2K-associated lab tests: urine protein/creatinine ratio
 - Urine biomarker (optional)
- 7. Perform SLEDAI-2K
- 8. Perform SLICC/ACR Damage Index
- 9. Assess worsening and/or flare of SLE disease activity using SLE Increase in Disease Activity CRF and complete for SLE related AEs that are not serious, if applicable
- 10. Evaluate subject for signs and symptoms of TB using a TB surveillance form
- 11. Assess for AEs/SAEs/AESIs (nonserious AEs will only be captured during the first year of the subject's participation in the study; however, nonserious AEs that result in interruption of investigational product and/or discontinuation from the study will be captured at any time during the subject's participation in the study)

5.1.4 Unscheduled Visit

- 1. Perform physical examination (if applicable, record new findings as AEs or SAEs)
- 2. Record concomitant medications
- 3. Take vital signs
- 4. Collect blood samples for:
 - Serum chemistry
 - Hematology
 - Lipid profile (Subjects will be required to fast for at least 8 hours prior to this assessment. If a subject has not fasted, the assessment should be performed under fasted conditions at the next visit)
 - SLEDAI-2K-associated lab tests (C3, C4, CH50, anti-dsDNA)
 - Pharmacokinetics (MEDI-546 serum concentration)
 - Immunogenicity (ADA to MEDI-546)
- 5. Collect urine sample for:
 - Urinalysis
 - Urine β-HCG (if appropriate; dipstick; females of childbearing potential only, ensure result is negative)
 - SLEDAI-2K-associated lab tests: urine protein/creatinine ratio
 - Urine biomarker (optional)
- 6. Perform SLEDAI-2K
- 7. Perform SLICC/ACR Damage Index
- 8. Assess worsening and/or flare of SLE disease activity using SLE Increase in Disease Activity CRF and complete for SLE related AEs that are not serious, if applicable
- 9. Evaluate subject for signs and symptoms of TB using a TB surveillance form
- 10. Assess for AEs/SAEs/AESIs (nonserious AEs will only be captured during the first year of the subject's participation in the study; however, nonserious AEs that result in interruption of investigational product and/or discontinuation from the study will be captured at any time during the subject's participation in the study)

5.2 Description of Study Procedures

A Laboratory Manual will be provided to the sites that specifies the procedures for collection, processing, storage, and shipment of samples, as well as laboratory contact information, specific to this clinical research study.

5.2.1 Medical History

A complete medical history by body system will be documented for each subject and will include any viral reactivation events as well as the subject's full SLE and non-SLE history. The SLE history includes all previous manifestations of SLE including SLE medication history. Only new events or worsening of previous events that occur between Day 422 of Study CD-IA-MEDI-546-1013 and prior to signing of informed consent of Study CD-IA-MEDI-546-1145 should be recorded in the Medical History CRF. On Day 1, the medical history will be reviewed and any changes will be documented, if applicable.

5.2.2 Physical Examination, ECG, Weight, Cushingoid Features, and Pap Smear

A complete physical examination will be performed at intervals designated in the schedule of study procedures and include the following examinations: head, eyes, ears, nose and throat, lungs, heart, abdomen, joints, muscles and soft tissues, neurologic system, skin, and lymph nodes; body weight will be captured according to the Schedule of Study Procedures (Table 5.1-1). Medically significant changes from Day 1 physical examination will be recorded as AEs.

A computerized 12-lead ECG will be performed according to the Schedule of Study Procedures (Table 5.1-1 and Table 5.1-2). The investigator or qualified designee will review and indicate if the ECG is normal or abnormal. Any medically significant changes from the Study CD-IA-MEDI-546-1013 Day 396 ECG will be recorded as an AE.

Subjects will be assessed for Cushingoid features at Day 1 (if appropriate) and at Q48W. Features, such as moon face, buffalo hump, purple or violaceous striae, central obesity, hirsutism, acne, easy bruising, and fragile skin, will be captured separately to evaluate whether resolution of same can occur over time with OCS reduction.

A Pap smear will be performed in females only at Week 144 (Visit 37). Subjects with an abnormal Pap smear result of high-grade squamous intraepithelial lesion (CIN-3/CIN III carcinoma in situ) or endocervical adenocarcinoma in situ will discontinue investigational product. In the event a female subject discontinues prematurely, a repeat Pap smear must be performed as part of the Early Discontinuation Visit.

5.2.3 Vital Signs

Vital signs (temperature, BP, pulse rate, and respiratory rate) will be obtained at each study visit. On infusion days, subjects will be monitored for vital signs taken in a sitting position at the following times:

- Shortly before the IV infusion (within 15 minutes of the beginning of the infusion)
- Every 15 (± 5) minutes during the infusion
- Immediately after completion of MEDI-546 infusion, including post-dose saline flush (within 15 minutes [± 5] after completion of MEDI-546 infusion)
- At 30 (± 5) and 60 (± 5) minutes after completion of MEDI-546 infusion, and every 30 (± 5) minutes thereafter or until stable and ready for discharge (as judged by the investigator).

If anaphylaxis, a hypersensitivity reaction, or an infusion-related reaction occurs during the IV infusion, vital signs will be taken more frequently, based on investigator judgment and as warranted by the severity of the reaction (see Section 4.5.6.1).

5.2.4 Tuberculosis Testing

A QFT-GIT will be performed at Day 1 for all subjects who tested negative or indeterminate at Day 337 in Study CD-IA-MEDI-546-1013. If a subject missed being tested at Day 1, a QFT-GIT should be performed at the next scheduled visit and then per protocol. An annual TB screen is not required for subjects who have tested positive and have been treated for latent TB in Study CD-IA-MEDI-546-1013.

Upon approval of Study CD-IA-MEDI-546-1145 Protocol Amendment 4, any subject whose last QFT-GIT result was negative or indeterminate (whether in this study or in Study CD-IA-MEDI-546-1013) and has not had a QFT-GIT performed in the previous year (from local approval date) should have it performed at the next scheduled visit and then per protocol.

All subjects must be evaluated by the physician for clinical signs/symptoms of active TB prior to each scheduled infusion visit using a TB surveillance form. If the evaluation raises suspicion that a subject may have a new or reactivated TB, an immediate and thorough investigation should be undertaken, including where possible, consultation with experts specializing in TB. Please note that TB in immunocompromised subjects may present as disseminated disease or with extrapulmonary features and should be referred for appropriate treatment.

5.2.4.1 Indeterminate Results

A newly indeterminate QFT-GIT test at Day 1 for subjects who had a negative result in Study CD-IA-MEDI-546-1013 must be repeated as soon as possible at least one time by the central laboratory. If the result remains indeterminate, a chest radiograph shows no evidence of active TB, there are no signs or symptoms of active TB, no recent contact with anyone

with active TB, and there is no history of latent (unless diagnosed with documentation of completion of appropriate treatment) or active TB, the subject may be enrolled in Study CD-IA-MEDI-546-1145. The subject will have additional QFT-GIT testing performed Q12W if the result remains indeterminate. If the subject has been in contact with anyone with active TB, or if the subject shows signs or symptoms of active TB, the subject should be referred to a physician specializing in TB to undergo additional evaluation prior to randomization and, if warranted, receive appropriate treatment for latent TB at or before the first administration of investigational product.

A QFT-GIT test will be performed at Day 1 for subjects whose results in Study CD-IA-MEDI-546-1013 were indeterminate and remain indeterminate in this study. If the result remains indeterminate, the chest radiograph from Study CD-IA-MEDI-546-1013 shows no evidence of active TB, there are no signs or symptoms of active TB, there has been no recent contact with anyone with active TB, and there is no history of latent (unless diagnosed with documentation of completion of appropriate treatment) or active TB, the subject may be enrolled in Study CD-IA-MEDI-546-1145. The subject will have additional QFT-GIT testing performed Q12W if the result remains indeterminate. If the subject has been in contact with anyone with active TB, or if the subject shows signs or symptoms of active TB, the subject should be referred to a physician specializing in TB to undergo additional evaluation prior to randomization and, if warranted, receive appropriate treatment for latent TB at or before the first administration of investigational product.

5.2.4.2 Positive Results

If, during the study, a subject is determined to have a positive QFT-GIT test result, the local country guidelines should be consulted for acceptable anti-TB treatment regimens. If no local guidelines exist for immunocompromised individuals, then USA guidelines must be followed:

To aid in the early detection of new or reactivated TB, subjects will be evaluated for signs and symptoms of TB at every visit (prior to drug infusion) using a TB surveillance form. If the evaluation raises suspicion that a subject may have a new or reactivated TB infection, an immediate and thorough investigation should be undertaken, including where possible, consultation with experts specializing in TB. Please note that TB in immunocompromised subjects may present as disseminated disease or with extrapulmonary features and should be referred for appropriate treatment. A subject must be withdrawn from study treatment if they are diagnosed with active TB, if they prematurely discontinue treatment for latent TB, or if they are noncompliant with latent TB treatment.

5.2.5 Clinical Laboratory Tests

Clinical laboratory safety tests will be performed in a central clinical laboratory. Urine pregnancy tests may be performed at the site using a licensed test (dipstick). Abnormal laboratory results should be repeated as soon as possible (preferably within 24 to 48 hours).

Subjects will be required to fast for at least 8 hours prior to the assessment of lipid profile (high-density lipoprotein [HDL], low-density lipoprotein [LDL], cholesterol, and triglycerides) according to the Schedule of Study Procedures (Table 5.1-1 and Table 5.1-2).

The following clinical laboratory tests will be performed (see Table 5.1-1 and Table 5.1-2 for the schedule of tests):

Serum Chemistry

- Calcium
- Chloride
- Potassium
- Sodium
- Aspartate transaminase (AST)
- Alanine transaminase (ALT)
- Alkaline phosphatase (ALP)

- Gamma glutamyl transferase (GGT)
- Blood urea nitrogen (BUN)
- Creatinine
- Total bilirubin (reflexively fractionated if elevated)
- Glucose
- Albumin
- Creatine kinase (CK)

Note for serum chemistries: Tests for AST, ALT, ALP, and total bilirubin must be conducted concurrently and assessed concurrently.

Hematology

- White blood cell (WBC) count with differential
- Red blood cell (RBC) count
- Hematocrit
- Hemoglobin

- Platelet count
- Mean corpuscular volume (MCV)
- Mean corpuscular hemoglobin concentration (MCHC)

Urinalysis

- Color
- Glucose

Ketones

Blood

- Appearance
- Specific gravity
- pH
- Bilirubin
- Protein
- Microscopy including WBC/high power field (HPF), RBC/HPF

Pregnancy Test (females of childbearing potential only)

• Urine human chorionic gonadotropin (HCG)

Note: Any female subject who is postmenopausal based on documented results from the serum follicle-stimulating hormone test will not require urine HCG tests in this study. Any female subject who feels that they have had a change in status to postmenopausal at any point during this study can request a serum follicle-stimulating hormone test. If the results show that the subject is postmenopausal, then the subject will not require any further urine HCG tests.

Additional Tests

- Lipid profile (HDL, LDL, cholesterol, triglycerides, direct LDL when triglycerides are > 400 mg/dL) requiring a fasting blood sample of at least 8 hours
- Immunology profile: ANA, extractable nuclear antigen (RNP, Sm, SSA, SSB), quantitative immunoglobulins
- Isolated HBc with HBV DNA detected by reflex testing at any time during Study CD-IA-MEDI-546-1013 or at any time for the duration of this study. To remain eligible for this study, the subject's HBV DNA levels should remain undetectable as per the central lab (ie, < 29 IU/mL HBV DNA detected).

Anti-dsDNA

Urine protein/creatinine ratio

SLEDAI-2K-related Laboratory Tests

- C3
- C4

- •
- CH50 complement

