4.2.1 Inclusion Criteria

Subjects must meet *all* of the following criteria:

- 1. Written informed consent and any locally required authorization (eg, HIPAA in the USA, EU Data Privacy Directive in the EU) obtained from the subject prior to performing any protocol-related procedures, including Day 1 evaluations.
- 2. Must have qualified for and received investigational product (MEDI-546 or placebo) and completed the treatment period plus the follow-up period (through Day 422) in Study CD-IA-MEDI-546-1013. Subjects who discontinued from Study CD-IA-MEDI-546-1013 are not eligible for this study, with the exception of those subjects in the regions of Donetsk and Lugansk in the Ukraine, where the political situation necessitated a suspension of study activities, and all other inclusion and exclusion criteria were met.
- 3. Females of childbearing potential who are sexually active with a nonsterilized male partner must use 2 methods of effective contraception for 28 days prior to Day 1, and must agree to continue using such precautions for 85 days after the final dose of investigational product; cessation of contraception after this point should be discussed with a responsible physician. Subjects must continue the use of their effective contraception as used in Study CD-IA-MEDI-546-1013. Periodic abstinence, the rhythm method, and the withdrawal method are not acceptable methods of contraception.
 - Females of childbearing potential are defined as those who are not surgically sterile (ie, bilateral tubal ligation, bilateral oophorectomy, or complete hysterectomy).
 - Postmenopausal is defined as 12 months with no menses without an alternative medical cause.

- Subjects must use 2 acceptable methods of effective contraception as described in Table 4.2.1-1.
- 4. Nonsterilized males who are sexually active with a female partner of childbearing potential must use 2 acceptable methods of effective contraception (see Table 4.2.1-1) from Day 1 for 85 days after receipt of the final dose of investigational product.

Table 4.2.1-1	Effective Methods of Contraception (Two Methods Must be
	Used)

	Barrier Methods		Intrauterine Device Methods		Hormonal Methods
•	Male condom plus	•	Copper T	•	Implants
	spermicide	•	Progesterone T ^a	•	Hormone shot or injection
•	Cap plus spermicide	•	Levonorgestrel-releasing	•	Combined pill
•	Diaphragm plus spermicide		intrauterine system (eg, Mirena [®]) ^a	•	Minipill
				•	Patch

^a This is also considered a hormonal method.

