4.5.5 Treatment Administration

The first day of dosing is considered Day 1.

Every dose of investigational product should be administered using the following guidelines:

- Females of childbearing potential must have a negative urine pregnancy test prior to receiving investigational product.
- MEDI-546 must be administered at room temperature by controlled infusion via an infusion pump into a peripheral vein. A physician must be present at the site or immediately available to respond to emergencies during all administrations of investigational product.
- MEDI-546 does not contain preservatives and any unused portion must be discarded. The dose of MEDI-546 must be prepared using aseptic technique. Total in-use storage time from needle puncture of the first vial of MEDI-546 for investigational product preparation to start of administration should not exceed 4 hours at room temperature or

24 hours at 2°C-8°C (36°F to 46°F). If storage time exceeds these limits, a new dose must be prepared from new vials.

- Administration should be performed using an extension line with a low protein-binding 0.2-µm in-line filter. The entire contents of the IV bag should be administered using an infusion pump over at least 30 minutes.
- MEDI-546 should be administered over at least 30 minutes. If a subject has a history of infusion reactions, MEDI-546 administration may be lengthened per the investigator's discretion. The subject's vital signs (temperature, blood pressure [BP], pulse rate, and respiratory rate) should be taken after the first 15 (± 5) minutes of infusion of investigational product into the subject and the subject should be assessed for signs of an infusion reaction.
- Immediately following the initial dosing, up to an additional 25 mL of saline will be given via infusion pump at the same pump speed utilized at the completion of the initial dosing.
- The duration of the MEDI-546 infusion and duration of MEDI-546 administration will be calculated as follows:
 - **Duration of Infusion:** The amount of time elapsed from the infusion start time to the infusion stop time. Infusion start time is defined as the time point where MEDI-546 is first infused into the subject. Infusion stop time is defined as the time point where the infusion pump completes infusion of MEDI-546, not including the saline flush.
 - For example: An infusion with a start time of 12:00 PM would have a duration of infusion recorded as at least 30 minutes (a time of at least 12:30 PM).

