 - Urine β-HCG (dipstick; females of childbearing potential only, ensure result is negative)
- 4. Assess worsening and/or flare of SLE disease activity using SLE Increase in Disease Activity CRF and complete for SLE related AEs that are not serious, if applicable
- 5. Evaluate subject for signs and symptoms of TB using a TB surveillance form
- 6. Take vital signs before administration of investigational product (within 15 minutes of the beginning of the investigational product infusion)
- 7. Administer investigational product
 - Take vital signs (BP, pulse, respiration, and temperature) approximately every 15 (± 5) minutes during the infusion, immediately after completion of the infusion, approximately 30 (± 5) and 60 (± 5) minutes after completion of administration of

investigational product, and every 30 (\pm 5) minutes thereafter or until stable and ready for discharge (as judged by the investigator)

8. Assess for AEs/SAEs/AESIs (nonserious AEs will only be captured during the first year of the subject's participation in the study; however, nonserious AEs that result in interruption of investigational product and/or discontinuation from the study will be captured at any time during the subject's participation in the study)

5.1.2.3 Every 12 Weeks; Weeks 12, 24, 36, 48, 60, 72, 84, 96, 108, 120, 132, and 144 (Visits 4, 7, 10, 13, 16, 19, 22, 25, 28, 31, 34, and 37)

In addition to procedures and assessments performed Q4W, the following are to be performed **every 12 weeks (Q12W)**:

- 1. Collect **predose** blood samples for:
 - Serum chemistry
 - Hematology
 - QuantiFERON-TB Gold (QFT-GIT; TB testing, only if indeterminate at any visit during Study CD-IA-MEDI-546-1013)
 - SLEDAI-2K-associated lab tests (C3, C4, CH50, anti-dsDNA)
 - Pharmacokinetics (MEDI-546 serum concentration; Weeks 12, 24, 36 and 48 only)
 - Pharmacodynamics (type I IFN signature with 21-gene assay; Weeks 12, 24, 36 and 48 only)
 - Immunogenicity (ADA to MEDI-546; Weeks 12, 24, 36 and 48 only)
 - Proteomics/biomarkers (Weeks 12, 24 and 48 only; optional)
- 2. Collect urine sample for:
 - Urinalysis
 - SLEDAI-2K-associated lab tests: urine protein/creatinine ratio
 - Urine biomarker (optional)
- 3. Perform SLEDAI-2K

5.1.2.4 Every 24 Weeks; Weeks 24, 48, 72, 96, 120 and 144 (Visits 7, 13, 19, 25, 31, and 37)

- 1. Administer SF-36v2 (should be completed prior to any clinical assessments)

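### Protocol 5.2.5, as worded, lets a serum FSH result alone end urine pregnancy testing in women who do not yet meet the 4.2.1 definition of postmenopausal

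*Protocol*

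**What the plan says.** Four parts of the protocol bear on this.

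- **Definition of postmenopausal (4.2.1, inclusion criterion 3).** "Postmenopausal is defined as 12 months with no menses without an alternative medical cause". FSH is not mentioned.
- **Definition of childbearing potential (same criterion).** "Females of childbearing potential are defined as those who are not surgically sterile", followed by a list of surgical procedures. Postmenopausal women are not expressly taken out of the group.
- **Dosing rule (4.5.5), which applies to every dose.** "Females of childbearing potential must have a negative urine pregnancy test prior to receiving investigational product". It gives no exception. The visit instructions use the same group, for example at Day 1: "dipstick; females of childbearing potential only, ensure result is negative".
- **Waiver (5.2.5), in a note under the heading** "Pregnancy Test (females of childbearing potential only"). A female subject who "feels that they have had a change in status to postmenopausal at any point during this study can request a serum" FSH test. Then: "If the results show that the subject is postmenopausal, then the subject will not require any further urine HCG tests". The note gives no duration of amenorrhoea, does not ask whether there is another cause, does not refer to 4.2.1, and does not say when testing resumes.

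**The concern.** The protocol uses one term with two tests behind it. In 4.2.1 the test is a year of history with other causes excluded. In 5.2.5 it is what a blood result shows. A single blood sample cannot establish a year without menses, so a woman can pass the second test without passing the first.

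What is at stake is exposure in pregnancy. Section 4.2.3 makes pregnancy or a positive test a reason for permanent discontinuation, and 6.4.3.3 bars further doses. The dipstick before each infusion is the scheduled check that would find a pregnancy in time. If it is dropped too early, detection before the next infusion depends on clinical suspicion. No endpoint, analysis population or estimate is involved.

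**Working it through.** **Step 1: the two rules side by side.** There are two open questions of reading. The first is whether 5.2.5 rests on FSH alone or silently takes over the 4.2.1 definition. The second is whether childbearing potential covers every woman who is not surgically sterile (literal), or leaves out women who meet the postmenopausal definition (ordinary). All cells concern women who are not surgically sterile.

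| | Childbearing potential: ordinary reading | Childbearing potential: literal reading |
|---|---|---|
| 5.2.5 on FSH alone | 4.5.5 and 5.2.5 clash for women with a postmenopausal FSH result who do not meet 4.2.1 | Same clash, and also for women who do meet 4.2.1 |
| 5.2.5 takes over 4.2.1 | No clash | Clash only for women who do meet 4.2.1; nothing is waived early |

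The top row follows the words of 5.2.5, because the waiver turns on what the results show. Across that row, women short of the 4.2.1 definition are of childbearing potential on either reading. For them 4.5.5 requires the test and 5.2.5 waives it. This group is the substance of the point.

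**Step 2: size for one woman.** The inputs are dosing every 4 weeks (28 days), the last dose at Week 156 (Table 5.1-1), and 12 months taken as 365 days. The number of pre-dose tests waived before she could meet 4.2.1 is the days still needed divided by 28, rounded down.

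- Menses have just stopped: 365/28 = 13.04, so 13 tests.
- Six months of amenorrhoea already: 182.5/28 = 6.5, so 6 tests.
- Nine months already: 91.25/28 = 3.26, so 3 tests.

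The schedule leaves room for 13 if the FSH result comes no later than Week 104: (156 - 108)/4 + 1 = 13. After that, fewer tests remain. Two situations fall outside this clock: amenorrhoea with another medical cause, and menses that resume after the waiver. The documents give nothing from which to size either.

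**Step 3: what a missed test could mean.** If a woman exempted early conceives, each 4 weeks by which recognition falls behind the scheduled test means one more 300 mg infusion. Assumed delays of 4, 8 and 12 weeks give 4/4 = 1, 8/4 = 2 and 12/4 = 3 infusions. The delays are assumptions, and the documents do not give the number of women or any pregnancy rate.

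**The case against.** The strongest reply is that a defined term keeps its definition. Postmenopausal is defined once, in 4.2.1, and 5.2.5 uses the word. On that view FSH only documents a status already reached, the woman's own impression triggers nothing more than a blood test, and what is missing is a cross-reference. This reading is possible, but 5.2.5 makes the result itself the ground for stopping, and a site has no instruction to check the history first.

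A second reply is that 5.2.5 is the specific rule and 4.5.5 the general one, so sites would treat the note as an exception. That may settle which instruction a site follows. It does not make the exception safe for a woman short of the definition.

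A third reply stands in full: other safeguards remain. Testing is not forbidden, only not required. Section 5.1.4 keeps a urine test at unscheduled visits where appropriate. Women of childbearing potential who are sexually active with a nonsterilized male partner "must agree to continue using such precautions for 85 days after the final dose of investigational product", using two methods. Harm needs an early waiver, conception despite contraception, and late recognition.

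A reader might also infer that 4.5.5 and 5.2.5 conflict for every waived woman and for every remaining dose, which would be 33 pre-dose tests after Week 24, (156 - 28)/4 + 1, or 26 after Week 52, (156 - 56)/4 + 1. The documents do not support that as a measure of the gap. The postmenopausal definition sits within criterion 3 directly after the childbearing-potential definition and has no function there unless it marks women outside that group. On that ordinary reading, 4.5.5 does not reach a woman who meets the definition. For her, the literal reading leaves only a wording ambiguity.

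**Conclusion.** The point holds for a defined group: women who are not surgically sterile, have an FSH result read as postmenopausal, and have not met the 4.2.1 definition. For them the protocol both requires and waives the pre-dose test. The extent is about 13 four-weekly tests for a woman whose menses have just stopped, and fewer if she is already part of the way through the 12 months.

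This rests on reading 5.2.5 as written, with FSH as the sole condition. If sites read the 4.2.1 definition into it, no test is dropped early. The point is limited to FSH tests requested during the study; it makes no claim about FSH cut-offs or about exemptions carried over from the parent study. The number of women affected is probably small, and nothing in the analysis changes. It is a minor participant-safety correction, worth making because the two instructions concern whether a dose may be given.

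**What to change.** In 5.2.5, replace the waiver with wording such as: *Urine HCG tests may stop only when the subject meets the Section 4.2.1 definition of postmenopausal and this is confirmed by serum FSH. If menses resume, testing restarts at the next visit.*

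In 4.5.5, after the reference to females of childbearing potential, add: *(except those exempted under Section 5.2.5)*. This also removes the ambiguity over pre-dose testing for women who do meet the definition, whichever way childbearing potential is read. Section 4.2.1 can stay as it is, so the contraception rules do not change.

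The cost is a wording change in two sections and about 13 extra dipsticks per affected woman, one at each four-weekly visit until she meets the definition. Those visits are already scheduled, and no new procedure or staff is needed. Women who are postmenopausal by the protocol's own definition are still spared the tests.
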